2.3 Rationale for dose and regimen selection

The selected doses and regimen will be based on the dose ranges and regimen available in the parent study. The starting dose of pasireotide alone or in combination with another treatment for Cushing's Disease and Acromegaly, should be the same dose as that which the patient was receiving in the parent study at roll over. After the starting dose, changes to pasireotide dose, and/or any medication given in combination with pasireotide for Cushing's Disease or Acromegaly, will be based on the investigator's judgment, but must follow the dose ranges provided in the parent study. Please note combination treatment in this rollover trial is only allowable for Cushing's Disease and Acromegaly parent protocols.

Pasireotide will be provided as:

1. Pasireotide s.c. – to be administered subcutaneously two or three times a day depending on the parent study dosing.
2. Pasireotide LAR to be administered as intramuscular injection every 28 days.

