8.1 Adverse events

8.1.1 Definitions and reporting

An adverse event is defined as the appearance of (or worsening of any pre-existing) undesirable sign(s), symptom(s), or medical condition(s) that occur after patient's signed informed consent has been obtained.

Abnormal laboratory values or test results occurring after informed consent constitute adverse events only if they induce clinical signs or symptoms, are considered clinically significant, require therapy (e.g., hematologic abnormality that requires transfusion or hematological stem cell support), or require changes in study medication(s).

Any ongoing adverse events from the parent study will be captured as medical history in the roll-over database. Any AE that begins (or worsens) after signing of the informed consent for the roll-over and during the 30-day (or 28-day) or 84-day (12 week) safety follow up period defined in the parent protocol should be reported in both clinical databases.

Adverse event monitoring should be continued for at least 30 days for patients receiving the s.c. formulation and 84 days for those receiving the LAR formulation (or 5 half-lives), whichever is longer) following the last dose of study treatment. Adverse events (including lab abnormalities that constitute AEs) should be described using a diagnosis whenever possible, rather than individual underlying signs and symptoms. When a clear diagnosis cannot be identified, each sign or symptom should be reported as a separate Adverse Event.

Adverse events will be assessed according to the current version of Common Terminology Criteria for Adverse Events (CTCAE).

If CTCAE grading does not exist for an adverse event, the severity of mild, moderate, severe, and life-threatening, corresponding to Grades 1 - 4, will be used. CTCAE Grade 5 (death) will not be used in this study; rather, information about deaths will be collected through the EOT eCRF page.

The occurrence of adverse events should be sought by non-directive questioning of the patient (subject) during the screening process after signing informed consent and at each visit during the study. Adverse events also may be detected when they are volunteered by the patient (subject) during the screening process or between visits, or through physical examination, laboratory test, or other assessments. As far as possible, each adverse event should be evaluated to determine:

1. The severity grade (CTCAE Grade 1-4)
2. Its duration (start and end dates)

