- A single occurrence will be counted if there is ≤ 1 day gap between the end date of the preceding AE and the start date of the consecutive AE
- More than one occurrence will be counted if there is > 1 day gap between the end date of the preceding AE and the start date of the consecutive AE

For occurrence, the presence of at least one SAE / SAE suspected to be related to study treatment / non SAE has to be checked in a block e.g., among AE's in a \leq 1 day gap block, if at least one SAE is occurring, then one occurrence is calculated for that SAE.

The number of deaths resulting from SAEs suspected to be related to study treatment and SAEs irrespective of study treatment relationship will be provided by SOC and PT.

Adverse events of special interest / grouping of AEs

The specific categories of AEs of special interest list for SOM230 are listed in attachment 8.2.

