	Hyperglycaemia (PT)
	Hyperglycaemic hyperosmolar nonketotic syndrome (PT)

Category	Adverse Event Term
	Impaired fasting glucose (PT)
	Impaired insulin secretion (PT)
	Increased insulin requirement (PT)
	Insulin-requiring type 2 diabetes mellitus (PT)
	Ketoacidosis (PT)
	Ketonuria (PT)
	Ketosis (PT)
	Ketosis-prone diabetes mellitus (PT)
	Monogenic diabetes (PT)
	Type 1 diabetes mellitus (PT)
	Type 2 diabetes mellitus (PT)
AESI Hypocortisolism related AEs	Adrenal insufficiency (PT)
	Adrenal suppression (PT)
	Adrenocortical insufficiency acute (PT)
	Cortisol decreased (PT)
	Cortisol deficiency (PT)
	Cortisol free urine decreased (PT)
	Glucocorticoid deficiency (PT)
	Glucocorticoids decreased (PT)
	Secondary adrenocortical insufficiency (PT)
	Steroid withdrawal syndrome (PT)
AESI Hypotension related AEs	Blood pressure ambulatory decreased (PT)
	Blood pressure decreased (PT)
	Blood pressure diastolic decreased (PT)
	Blood pressure immeasurable (PT)
	Blood pressure orthostatic abnormal (PT)
	Blood pressure orthostatic decreased (PT)
	Blood pressure systolic decreased (PT)
	Hypotension (PT)
	Mean arterial pressure decreased (PT)
AESI Hypothyroidism related AEs	Blood thyroid stimulating hormone decreased (PT)
	Hypothyroidism (PT)
	Myxoedema (PT)
	Myxoedema coma (PT)
	Secondary hypothyroidism (PT)
	Thyroid dermatopathy (PT)
	Thyroid stimulating hormone deficiency (PT)
	Thyroxine free decreased (PT)
	Tri-iodothyronine decreased (PT)
	Tri-iodothyronine free decreased (PT)

Category	Adverse Event Term
AESI Injection site reaction related AEs	Administration site abscess (PT)
	Immediate post-injection reaction (PT)
	Injection site atrophy (PT)
	Injection site bruising (PT)
	Injection site discolouration (PT)
	Injection site discomfort (PT)
	Injection site erosion (PT)
	Injection site erythema (PT)
	Injection site exfoliation (PT)
	Injection site granuloma (PT)
	Injection site haematoma (PT)
	Injection site haemorrhage (PT)
	Injection site hypersensitivity (PT)
	Injection site inflammation (PT)
	Injection site irritation (PT)
	Injection site necrosis (PT)
	Injection site nodule (PT)
	Injection site oedema (PT)
	Injection site pain (PT)
	Injection site pruritus (PT)
	Injection site rash (PT)
	Injection site reaction (PT)
	Injection site swelling (PT)
	Injection site urticaria (PT)
ESI Liver safety related AEs	Alanine aminotransferase abnormal (PT)
	Alanine aminotransferase increased (PT)
	Ammonia increased (PT)
	Aspartate aminotransferase abnormal (PT)

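### The closed list of injection-site AESI terms has no injection-site abscess, infection or cellulitis term, so that one AESI category may be undercounted

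*SAP*

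**What the plan says.** SAP 7.4.1 summarises and lists AESI separately, with all grades beside grade 3 or 4. It defines the categories by reference only: "The specific categories of AEs of special interest list for SOM230 are listed in attachment 8.2". SAP 7.1.1, on the primary endpoint, names AESI together with AEs and SAEs as the basis of the safety assessment.

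In SAP 8.2 the injection-site group holds 24 preferred terms (PTs). One is "Administration site abscess (PT", one is an immediate post-injection reaction, and the other 22 all begin with the words Injection site. Those 22 include "Injection site necrosis (PT", "Injection site erosion (PT", "Injection site nodule (PT" and "Injection site granuloma (PT". They also include mild terms such as bruising, discomfort and discolouration, and the general term for an injection site reaction.

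Both formulations are injected. Protocol 2.3 gives the s.c. form two or three times a day, and for the depot form it says: "Pasireotide LAR to be administered as intramuscular injection every 28 days". On reporting, Protocol 8.1.1 says that events "should be described using a diagnosis whenever possible, rather than individual underlying signs and symptoms".

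SAP 7.4.1 codes with whichever MedDRA version is newest at analysis. It gives no step for reconciling the fixed list with that version.

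**The concern.** The list is the whole definition of the category: an event counts only if its PT is on it. An abscess term is present, but in its route-unspecific form, while almost every other entry is specific to injection. For a drug given only by injection, one would expect local infection to be listed under injection-site names as well.

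The reporting rule in Protocol 8.1.1 adds to this. A site that follows it would report an infected injection site as an abscess or cellulitis rather than as pain, swelling or erythema. The last three are on the list. The first two are not, apart from the generic abscess term. Good reporting practice could therefore move an event out of the category.

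At stake is one row of the AESI table in a long-term safety study that is also classed as a voluntary PASS (SAP 2.3). Any error from this source goes one way, towards too few patients with an injection-site AESI.

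**Working it through.** The plan states no figure to reproduce, and no hypothesis is tested (Protocol 10.4.2, SAP 7.1.2). The check is a count and a comparison of the text.

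**1. Count the group (SAP 8.2).** 1 (administration site abscess) + 1 (immediate post-injection reaction) + 22 (terms beginning Injection site) = 24.

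**2. Search the 24 terms.**

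| Word sought | Matches |
|---|---|
| abscess | 1 (administration site only) |
| infection | 0 |
| cellulitis | 0 |
| induration | 0 |
| mass | 0 |
| necrosis | 1 |
| nodule | 1 |
| granuloma | 1 |

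**3. Rule out a text-reading loss.** The 24 terms are in strict alphabetical order, with no page break inside the group. The five absent terms would belong at four separate places:
- abscess, before atrophy;
- cellulitis, between bruising and discolouration;
- induration and infection, between hypersensitivity and inflammation;
- mass, between irritation and necrosis.

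One lost block could not explain all five, so the absences are in the plan itself.

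**4. Look for another home.** No other AESI category in SAP 8.2 lists an injection-site or skin-infection term. An event left out here is not picked up by another AESI group.

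**5. Trace one event through the planned outputs.** Suppose a patient's only local event is coded to an injection-site abscess PT that exists but is not listed.

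| Output (SAP 7.4.1) | Counted? |
|---|---|
| Injection-site AESI, all grades | No |
| Injection-site AESI, grade 3 or 4 | No |
| All treatment-emergent AEs, by system organ class and/or PT and by grade | Yes |
| Same summary for SAEs, if serious | Yes |
| AEs leading to discontinuation, dose change or added therapy, if applicable | Yes |
| AE and SAE listings | Yes |

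**6. Size.** If k patients have only unlisted injection-site events and the Safety Set has N patients, the category percentage is too low by 100k/N points. The documents give no rate from which to estimate k, and no final N. For scale only, the Amendment 2 rationale reports 301 enrolled. With that as N, one patient is 100 × 1/301 = 0.33 points. In the breakdowns by indication and formulation, where the denominators are smaller, one patient weighs more. If k = 0, nothing changes.

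**The case against.** The strongest reply is that the decisive step lies outside the documents. Neither contains the MedDRA hierarchy, and the SAP names no version. Protocol 8.1.1 governs what investigators report, not the PT to which a report is coded. If a local infection coded to a listed term, nothing would be lost. This stands, and it makes the conclusion conditional. The list offers only indirect support for the condition: 22 separate injection-site PTs suggest that local events are coded finely by site.

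The selection may also be deliberate. Protocol 8.1.3 says AESI are set by ongoing review of the safety data and refers to the Investigator Brochure, which is not available here. That also stands as a possibility. One should not claim that the generic abscess term proves an intention to cover every abscess. But the SAP gives no reason for leaving local infection out while counting bruising.

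A reader might infer that the most serious local reactions drop out. The documents do not support that. Necrosis, erosion, hypersensitivity and one abscess term are listed. Nothing ranks induration or mass among the most serious reactions, and their near neighbours nodule, granuloma and swelling are present.

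A reader might also infer that abscesses could go unseen, or that the primary endpoint is biased. That does not follow either. The endpoint in Protocol Table 3-1 and SAP Table 5-1 is the frequency and severity of AEs and SAEs, and these events remain in those tables and listings by their own PT and, in the AE and SAE summaries, by grade.

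**Conclusion.** The concern holds in a limited form. The absence of injection-site abscess, infection, cellulitis, induration and mass from the list is certain. The undercount is conditional on two things: that these are separate PTs in the MedDRA version used, and that at least one patient has such an event and no listed one. If both are true, the injection-site AESI category is too low, in the all-grades column and, for grade 3 or 4 events, in that column too. Its size cannot be given from the documents.

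The effect stops at that category. AESI are named under the primary endpoint in SAP 7.1.1, so the category is worth getting right, but overall AE and SAE results do not depend on it. The case is strongest for the three infection terms and weaker for induration and mass.

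**What to change.** Before database lock:

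1. Have the coding team check the injection-site group in SAP 8.2 against every injection-site PT in the MedDRA version used for the analysis, and record the result.
2. Add the injection-site abscess, infection and cellulitis terms where they exist as PTs, or state why they are left out.
3. Consider induration and mass as lower-priority additions, since nodule, granuloma and swelling are already there.
4. Keep the administration site abscess term.
5. Rerun the AESI flag and the outputs that use it.

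The cost is a few lines in a SAP attachment and one rerun, with no new data and no change to patient management. The reported percentage for the category may rise slightly. There is a small loss of comparability with any earlier interim output that used the present list, which a footnote naming the added terms would cover.

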8.1.2 Laboratory test abnormalities

8.1.2.1 Definitions and reporting

Laboratory abnormalities that constitute an Adverse event in their own right (are considered clinically significant, induce clinical signs or symptoms, require concomitant therapy or require changes in study treatment), should be recorded on the Adverse Events CRF. Whenever possible, a diagnosis, rather than a symptom should be provided (e.g. anemia instead of low hemoglobin). Laboratory abnormalities that meet the criteria for Adverse Events should be followed until they have returned to normal or an adequate explanation of the abnormality is found. When an abnormal laboratory or test result corresponds to a sign/symptom of an already reported adverse event, it is not necessary to separately record the lab/test result as an additional event.

Laboratory abnormalities, that do not meet the definition of an adverse event, should not be reported as adverse events. A Grade 3 or 4 event (severe) as per CTCAE does not automatically indicate a SAE unless it meets the definition of serious as defined below and/or as per investigator's discretion. A dose hold or medication for the lab abnormality may be required by the protocol in which case the lab abnormality would still, by definition, be an adverse event and must be reported as such.

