14.2 Appendix 2: Recommended hepatic safety management guidance

Patients with transaminase increase combined with TBIL increase may be indicative of potential DILI, and should be considered as clinically important events.

If any of the criteria below are observed at any routine examinations (standard of care),

- ALT or AST $> 3 \times$ ULN and Total Bilirubin $\geq 2 \times$ ULN.
- ALT or AST $> 5 \times$ ULN and $\leq 8 \times$ ULN.
- ALT or AST $> 8 \times$ ULN, patient should be discontinued.

The following should be performed immediately within **72 hours** of awareness of the abnormality (for further details refer to [Figure 14-1](#)):

- Perform liver-directed medical history and physical examination (i.e. assess occupational hazards, concomitant medications including OTC meds, inter-current illness, etc).
- Liver chemistry tests: ALT, AST, total bilirubin, (fractionate to direct/indirect bilirubin if total bilirubin is $> 2.0 \times$ ULN), Alb, PT (INR), ALP, and GGT.
- Perform hepatitis screen: anti-HAV, IgM (to confirm acute Hepatitis A), HbsAg, Anti-HBc, anti-HCV (if positive, PCR viral load should be assessed), Anti-HEV, ANA antibodies, anti-smooth muscle anti-bodies, CMV and EBV.
- Perform abdominal ultrasound (liver and biliary tree).

[figure not shown]
Liver chemistry tests (LFTs) should be monitored every **3-4 days** until resolution or return to baseline status.

Patients or subjects may need to be discontinued if the abnormal liver function criteria are met upon LFT retesting. Progress reports of the event should be maintained until resolution or stabilization (i.e. no further elevation after 2 consecutive assessments).

For ALT or AST $> 5 \times$ ULN and $\leq 8 \times$ ULN, the following must occur (in addition to the safety follow up procedures noted above).

- Study medication should be temporarily interrupted and liver chemistry tests monitored every **3-4 days** until resolution or return to baseline.
- If resolution (ALT and AST ≤ 5 ULN) or return to baseline does not occur after 2 weeks, the patient should be discontinued.
- If ALT or AST return to less than 5 x ULN study drug can be resumed and patient can continue study per protocol.
- If ALT or AST rises above 5 x ULN any time after study drug is resumed, then study drug should be discontinued immediately.

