8.2 LIST OF AES OF SPECIAL INTEREST

Category	Adverse Event Term
	Bile output abnormal (PT)
	Bile output decreased (PT)
	Bile output increased (PT)
	Biliary cirrhosis (PT)
	Biliary colic (PT)
	Biliary dilatation (PT)
	Biliary dyskinesia (PT)
	Biliary dyspepsia (PT)
	Biliary fibrosis (PT)
	Biliary fistula (PT)
	Biliary ischaemia (PT)
	Biliary tract disorder (PT)
	Bilirubin conjugated abnormal (PT)
	Bilirubin conjugated increased (PT)
	Bilirubin excretion disorder (PT)
	Bilirubin urine present (PT)
	Bilirubinuria (PT)
	Blood alkaline phosphatase abnormal (PT)
	Blood alkaline phosphatase increased (PT)
	Blood bilirubin abnormal (PT)
	Blood bilirubin increased (PT)
	Blood bilirubin unconjugated increased (PT)
	Cholangiogram abnormal (PT)
	Cholecystectomy (PT)
	Cholecystitis (PT)
	Cholecystitis acute (PT)
	Cholecystitis chronic (PT)
	Cholecystogram intravenous abnormal (PT)
	Cholecystogram oral abnormal (PT)
	Cholelithiasis (PT)
	Cholelithiasis migration (PT)
	Cholelithiasis obstructive (PT)
	Cholestasis (PT)
	Deficiency of bile secretion (PT)
	Endoscopy biliary tract abnormal (PT)
	Gallbladder disorder (PT)
	Gallbladder enlargement (PT)
	Gallbladder fibrosis (PT)
	Gallbladder fistula (PT)
	Gallbladder hypofunction (PT)

Category	Adverse Event Term
category	Gallbladder necrosis (PT)
	Gallbladder obstruction (PT)
	Gallbladder oedema (PT)
	Gallbladder operation (PT)
	Gallbladder operation (FT)
	Haemohilia (PT)
	Henatitis cholestatic (PT)
	Hepatobiliary disease (PT)
	Hyperbilirubinaemia (PT)
	laundice (PT)
	Jaundice cholestatic (PT)
	Jaundice extrahepatic obstructive (PT)
	Obstructive pancreatitis (PT)
	Perforation bile duct (PT)
	Pseudocholelithiasis (PT)
	Ultrasound biliary tract abnormal (PT)
	Urine bilirubin increased (PT)
	X-ray hepatobiliary abnormal (PT)
AESI Growth hormone deficiency related AEs	Blood growth hormone decreased (PT)
,	Insulin-like growth factor decreased (PT)
AESI Hyperglycemia-related AEs	Blood glucose increased (PT)
	Blood insulin decreased (PT)
	Diabetes mellitus (PT)
	Diabetes mellitus inadequate control (PT)
	Diabetes with hyperosmolarity (PT)
	Diabetic coma (PT)
	Diabetic hyperglycaemic coma (PT)
	Diabetic hyperosmolar coma (PT)
	Diabetic ketoacidosis (PT)
	Diabetic ketoacidotic hyperglycaemic coma (PT)
	Diabetic ketosis (PT)
	Fructosamine increased (PT)
	Glucose tolerance decreased (PT)
	Glucose tolerance impaired (PT)
	Glucose tolerance test abnormal (PT)
	Glucose urine (PT)
	Glycosuria (PT)
	Glycosylated haemoglobin increased (PT)

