	Aspartate aminotransferase increased (PT)
	Blood cholinesterase abnormal (PT)
	Blood cholinesterase decreased (PT)
	Computerised tomogram liver abnormal (PT)
	Gamma-glutamyltransferase abnormal (PT)
	Gamma-glutamyltransferase increased (PT)
	Guanase increased (PT)
	Hepatic enzyme abnormal (PT)
	Hepatic enzyme decreased (PT)
	Hepatic enzyme increased (PT)
	Hepatic function abnormal (PT)
	Hepatobiliary scan abnormal (PT)

Category	Adverse Event Term
	Hyperammonaemia (PT)
	Hypertransaminasaemia (PT)
	Liver function test increased (PT)
	Transaminases abnormal (PT)
	Transaminases increased (PT)
	Ultrasound liver abnormal (PT)
	Urine bilirubin increased (PT)
AESI Low blood cell related AEs	Anaemia (PT)
	Febrile neutropenia (PT)
	Haematocrit decreased (PT)
	Haemoglobin decreased (PT)
	Leukopenia (PT)
	Lymphocyte count decreased (PT)
	Lymphopenia (PT)
	Neutropenia (PT)
	Platelet count decreased (PT)
	Red blood cell count decreased (PT)
	Thrombocytopenia (PT)
AESI Pancreatitis related AEs	Abdominal compartment syndrome (PT)
	Blood trypsin increased (PT)
	Fat necrosis (PT)
	Hyperlipasaemia (PT)
	Lipase abnormal (PT)
	Lipase increased (PT)
	Pancreatic enzyme abnormality (PT)
	Pancreatic enzymes abnormal (PT)
	Pancreatic enzymes increased (PT)
	Pancreatitis (PT)
	Pancreatitis acute (PT)
	Pancreatitis haemorrhagic (PT)
	Pancreatitis necrotising (PT)
	Pancreatitis relapsing (PT)
	Peripancreatic fluid collection (PT)
AESI QT-prolongation-related AEs	Cardiac arrest (PT)
	Cardiac death (PT)
	Cardiac fibrillation (PT)
	Cardio-respiratory arrest (PT)
	Electrocardiogram QT interval abnormal (PT)
	Electrocardiogram QT prolonged (PT)
	Electrocardiogram repolarisation abnormality (PT)

Category	Adverse Event Term
	Long QT syndrome (PT)
	Loss of consciousness (PT)
	Sudden cardiac death (PT)
	Sudden death (PT)
	Syncope (PT)
	Torsade de pointes (PT)
	Ventricular arrhythmia (PT)
	Ventricular fibrillation (PT)
	Ventricular flutter (PT)
	Ventricular tachyarrhythmia (PT)
	Ventricular tachycardia (PT)

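### The liver AESI group in SAP 8.2 has no clinical liver diagnosis, so cases recorded only as a diagnosis can be missing from the liver AESI frequency

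*SAP*

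**What the plan says.** SAP 7.1.1 names AESIs, with AEs and SAEs, as a main basis of the primary safety assessment. SAP 7.4.1 gives AESIs their own summary and listing and takes the categories from attachment 8.2.

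In that attachment the liver group opens with "Alanine aminotransferase abnormal (PT" and closes with "Urine bilirubin increased (PT". Between them are enzyme, ammonia and cholinesterase terms, imaging findings such as "Computerised tomogram liver abnormal (PT", and one function term, "Hepatic function abnormal (PT". Jaundice terms, for example "Jaundice cholestatic (PT", are in the gallbladder and biliary group.

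On recording, Protocol 8.1.1 says that AEs, including laboratory abnormalities that qualify as AEs, "should be described using a diagnosis whenever possible, rather than individual underlying signs and symptoms". Protocol 8.1.2.1 repeats for laboratory abnormalities that, where possible, "a diagnosis, rather than a symptom should be provided". It adds that a laboratory result belonging to an event already reported need not be entered again.

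Protocol Appendix 2 states the hepatic concern: "Patients with transaminase increase combined with TBIL increase may be indicative of potential DILI". It regards such events as clinically important.

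**The concern.** The term list and the recording rule do not fit together. The list finds liver events through test findings, while the rule steers sites towards naming the disease. A patient whose event is entered as a raised transaminase is counted in the liver group. A patient whose event is recognised as drug-induced liver injury, and entered under that name alone, is not.

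At stake is the completeness of the one planned pooled view of liver safety. No laboratory analysis would fill the gap: Protocol 10.5.3.3 plans no other safety data, and the laboratory paragraph of SAP 4.1 covers pregnancy tests only. A reader of the study report who turns to the liver AESI row for the frequency of liver events could find a number that leaves out some diagnosed cases, with nothing on the table to say so.

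**Working it through.** The plan gives no figure to reproduce. The check is a count of terms, followed by tracing recorded terms through the groups.

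**1. Content of the liver group (SAP 8.2).**

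| Type | Terms | Count |
|---|---|---|
| Laboratory | ALT (2), AST (2), ammonia increased, hyperammonaemia, blood cholinesterase (2), gamma-glutamyltransferase (2), guanase, hepatic enzyme (3), hypertransaminasaemia, liver function test increased, transaminases (2), urine bilirubin increased | 19 |
| Imaging | CT of liver, hepatobiliary scan, liver ultrasound | 3 |
| Function | hepatic function abnormal | 1 |
| Clinical liver diagnosis | none | 0 |

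19 + 3 + 1 + 0 = 23. A search of the 23 terms for hepatitis, failure, injury, necrosis, cirrhosis, toxicity, jaundice, cholesta- and steatosis finds nothing.

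**2. Could rows have dropped out?** This is unlikely for the main diagnoses. The group is in unbroken alphabetical order. Drug-induced liver injury, hepatic failure, hepatitis and liver injury would each fall between two rows that stand next to each other. Only terms sorting between the hepatobiliary scan and hyperammonaemia rows, such as hepatocellular injury or hepatotoxicity, would fall at a page break.

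**3. Comparison with other groups in the attachment.** The pancreatitis group has 15 terms, of which 5 are pancreatitis diagnoses beside enzyme findings. The hyperglycemia group combines glucose and glycosylated haemoglobin findings with diagnoses such as type 2 diabetes and diabetic ketoacidosis. The liver group does not mix findings and diagnoses in this way.

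**4. Where a recorded term is counted.**

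| Term recorded by the site | Liver group | Any AESI group |
|---|---|---|
| ALT or AST increased | yes | yes |
| Urine bilirubin increased | yes | yes (also gallbladder/biliary) |
| Blood bilirubin increased, hyperbilirubinaemia | no | yes (gallbladder/biliary) |
| Jaundice, cholestasis, cholestatic hepatitis, biliary cirrhosis, hepatobiliary disease | no | yes (gallbladder/biliary) |
| Non-cholestatic hepatitis, drug-induced liver injury, hepatic failure | no | no |

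**5. Joining this to the recording rule.** Protocol 8.1.1 and 8.1.2.1 allow a site to enter one diagnosis and no accompanying laboratory event. If that diagnosis is in the last row of the table, the patient adds nothing to any AESI count. If it is in the row above, the patient counts, but not as a liver case, although Protocol 7.1.5.1 treats jaundice as a hepatic criterion.

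**6. Size.** The understatement equals the number of patients with an unlisted liver diagnosis and no separately recorded listed term. Neither document gives that number or anything from which to estimate it.

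**The case against.** The strongest reply is that little is lost. Under SAP 7.4.1 every treatment-emergent AE and SAE is tabulated by system organ class and preferred term, by grade and by relationship, and listed. AEs leading to discontinuation, dose change or additional therapy have their own tables, and SAP 7.4.2 covers deaths. A serious case of hepatic failure would appear there by name. No hypothesis is tested, so no inference changes. This stands, and it limits the point to the AESI summary.

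Three stronger readings are tempting, and the documents do not support them.

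- *Sites are told not to record the laboratory result.* Protocol 8.1.2.1 says only that a second entry is unnecessary, and the preference for a diagnosis applies where one is possible.
- *The better a site follows the protocol, the less likely a serious liver case is to be counted.* Protocol 8.1.2.1 also says that a laboratory abnormality for which the protocol requires a dose hold is an AE and must be reported. Appendix 2 requires an AE entry when its laboratory criteria are met and the investigator judges the finding to be an AE. These rules do not force a laboratory term where a diagnosis replaces it, but they leave compliant routes to a listed term. The combined transaminase and bilirubin rise described in Appendix 2, if entered as laboratory terms, is counted: the transaminase under liver, and a blood bilirubin term under gallbladder and biliary.
- *All liver diagnoses are missed, up to 100%.* Several are AESIs already, under gallbladder and biliary, and no calculation supports a percentage.

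It can also be said that the enzyme focus may be deliberate. Protocol 2.6 names transient transaminase elevation as an expected effect, and Protocol 8.1.3 refers to the Investigator Brochure for AESIs. The brochure is not among the documents, so this cannot be checked. Neither document explains why diagnoses are left out of this group but included in the pancreatitis and hyperglycemia groups.

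**Conclusion.** The point holds in a limited form. The liver AESI group has 23 terms and no clinical liver diagnosis. A case recorded only as non-cholestatic hepatitis, drug-induced liver injury or hepatic failure falls outside every AESI group. Cholestatic hepatitis, jaundice and the bilirubin terms other than urine bilirubin increased are counted only under gallbladder and biliary.

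The liver AESI frequency can therefore be too low for diagnosed cases. This conclusion assumes that at least some sites enter a diagnosis without a separate listed finding, which the recording rule permits. The extent is unknown, and it would be wrong to infer that serious liver cases disappear from the safety analysis. The defect is in one descriptive grouping, but that grouping feeds a named part of the primary safety assessment, so it is worth correcting.

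**What to change.** Before database lock, the point by which SAP section 2 says final-analysis decisions are to be made, add hepatic diagnosis preferred terms to the liver group in attachment 8.2. Examples are hepatitis, hepatocellular injury, drug-induced liver injury, hepatotoxicity and hepatic failure. Footnote the AESI tables to say that the group was extended.

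Cross-listing the jaundice and bilirubin terms in the liver group is optional, since they are already AESIs. It would put a combined transaminase and bilirubin case in one group. The attachment already allows a term to stand in two groups, as it does for urine bilirubin increased and for QT prolongation on the electrocardiogram.

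The cost is an edit to one attachment and to the term lookup behind the tables. Data collection and the analysis set are unaffected. The one drawback is that liver AESI counts may not be directly comparable with earlier interim reports if those used the present list. Showing the count under both the present and the extended list in the final report would deal with that.

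### SAP 8.2 counts Liver function test increased as a liver AESI but omits Liver function test abnormal, so an event coded to the latter would be missing from the liver AESI summary

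*SAP*

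**What the plan says.** SAP 7.1.1 makes AESIs part of the primary safety assessment, alongside AEs and SAEs. SAP 7.4.1 has them listed and summarized separately, for all grades and for grade 3 or 4, and takes the AESI categories from attachment 8.2. Each row of that attachment is a term tagged as a PT. SAP 7.4.1 codes events with the latest MedDRA version available at the time of analysis, so the list is not tied to a fixed version.

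The liver group, whose heading was read from the PDF as "ESI Liver safety related AEs", has 23 terms. Among them are "Liver function test increased (PT" and several non-directional laboratory terms: "Alanine aminotransferase abnormal (PT", "Aspartate aminotransferase abnormal (PT", "Blood cholinesterase abnormal (PT", "Gamma-glutamyltransferase abnormal (PT" and "Transaminases abnormal (PT", plus *Hepatic enzyme abnormal* and *Hepatic function abnormal*. *Liver function test abnormal* is in neither this group nor any other.

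The protocol describes liver findings in both ways. Appendix 2 states: "Patients or subjects may need to be discontinued if the abnormal liver function criteria are met upon LFT retesting". The dose-modification tables and their cross-references in the later appendices speak instead of an LFT increase.

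**The concern.** For most liver laboratory tests on the list, the sponsor counts the non-directional result as well as the directional one. The liver function test, the broadest laboratory term in the group, is counted only in its directional form, and the SAP gives no reason. Even *Hepatic enzyme decreased* is counted.

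Membership of the group depends on the coded PT. If the missing term is a PT of its own, two reports of the same kind of laboratory finding could be treated differently in the liver AESI table, depending on which of the two PTs each was coded to. Protocol 2.6 names transaminase elevation as an expected effect of pasireotide, and Protocol 7.1.5.1 has hepatic discontinuation criteria, so this AESI group will be read with attention.

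**Working it through.** The plan states no figure on this point, tests no hypothesis (SAP 7.1.2) and has no sample size calculation (Protocol 10.7). The check is therefore a comparison of terms.

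**Step 1: is the row really absent?** The 23 liver terms stand in alphabetical order. The missing term would fall between *Hypertransaminasaemia* and *Liver function test increased*, and no page break falls there. The attachment does show reading errors elsewhere (the group heading has lost its first letter), so a lost row cannot be fully excluded. Nothing at this place suggests one.

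**Step 2: which directional laboratory terms have an *abnormal* row?** Take every test in the liver group listed as *increased* or *decreased*:

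| Test | Directional form listed | *Abnormal* row |
|---|---|---|
| Alanine aminotransferase | increased | yes |
| Aspartate aminotransferase | increased | yes |
| Blood cholinesterase | decreased | yes |
| Gamma-glutamyltransferase | increased | yes |
| Hepatic enzyme | increased, decreased | yes |
| Transaminases | increased | yes |
| Ammonia | increased | no |
| Guanase | increased | no |
| Urine bilirubin | increased | no |
| Liver function test | increased | no |

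So 6 of 10 tests have the *abnormal* row and 4 do not. Leaving out the liver function test itself, 6 of the other 9 have it. Three terms cover more than one analyte: hepatic enzyme, transaminases and liver function test. The first two have the *abnormal* row and the third does not.

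**Step 3: when is a patient missed?** Let N be the Safety Set, L the number of patients with at least one treatment-emergent event coded to a listed liver PT, and M the number with a treatment-emergent event coded to *Liver function test abnormal* and no listed liver PT.

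- Liver AESI percentage as planned: 100 × L / N.
- With the term added: 100 × (L + M) / N.
- Difference: 100 × M / N, which is zero or positive because M cannot be negative.

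The direction is therefore known. The size is not: the documents give no adverse event data, so neither L nor M can be filled in, and M may be 0.

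**Step 4: effect of the addition on the list.** The group goes from 23 to 24 terms, and the tests with an *abnormal* row go from 6 of 10 to 7 of 10.

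**The case against.** The strongest case against the point has four parts.

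- **The list has no uniform pairing rule.** A reader might infer that every comparable laboratory term has its *abnormal* partner and that the liver function test is the only exception. Step 2 shows otherwise: ammonia, guanase and urine bilirubin are also *increased* only. In the gallbladder group, unconjugated blood bilirubin is likewise listed as *increased* only. An unpaired term does not by itself prove an error. This stands. What remains is the narrower contrast with the other two multi-analyte terms and the main liver enzymes.
- **The protocol does not steer sites to the missing term.** A reader might infer that a site reporting abnormal LFTs is repeating the protocol's own phrase. Appendix 2 attaches *abnormal* to liver function criteria and mentions LFTs only for the retest, and the recurring phrase elsewhere is an LFT increase, which matches the listed PT. The criteria in Appendix 2 are ALT and AST thresholds, one of them combined with bilirubin, and both enzymes are listed in both forms. Protocol 8.1.1 also asks for a diagnosis where possible. This stands.
- **Coding may take such reports to a listed term.** A reader might infer that reports of abnormal LFTs are simply not counted. The list works on coded PTs, not on reported wording, and such a report could be coded to *Hepatic function abnormal*, *Hepatic enzyme abnormal*, *Transaminases abnormal* or a specific enzyme. That *Liver function test abnormal* is a PT of its own cannot be verified from the documents either. This stands, and makes the point conditional.
- **Little is lost.** All treatment-emergent events remain in the tables by system organ class and preferred term and in the listings (SAP 7.4.1). Only the liver AESI summary is affected. Centers are pooled (SAP 4.1), so no comparison between sites is at risk. This also stands.

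None of the four gives a reason to leave the term out if it exists.

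**Conclusion.** This is a small gap in the AESI list that can be closed at almost no cost. As written, the liver group would not capture an event coded to *Liver function test abnormal*, while it does capture the corresponding non-directional result for ALT, AST, GGT, cholinesterase, hepatic enzyme and transaminases. The conclusion rests on one assumption: that this is a separate PT in the MedDRA version used. If it is not, nothing is lost.

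Any error runs in one direction, towards a lower liver AESI count. No number of patients can be attached to it. It is tempting to apply assumed rates to the 301 patients that the Amendment 2 rationale reports as enrolled. The documents support neither a rate of liver laboratory events nor a share coded to the missing PT, and 301 is an enrolment count from 2017 rather than the final Safety Set.

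**What to change.** Before database lock, which is the limit that the SAP introduction sets for decisions on the final analysis, have the coding team confirm whether *Liver function test abnormal* is a PT in the MedDRA version to be used. If it is, add it as a PT to the liver safety group in SAP 8.2.

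The cost is one added line in the attachment and a rerun of one AESI flag. No new data are needed and patient management is not affected. The liver AESI percentage may rise slightly, because the group would then be more complete.
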